## **6.2.5 Sponsor Responsibility for Reporting Adverse Events**

All Adverse Events will be reported to regulatory authorities, IRB/IECs and investigators in accordance with all applicable global laws and regulations.

## **7.0 STATISTICAL ANALYSIS PLAN**

This section outlines the statistical analysis strategy and procedures for the study. If, after the study has begun, changes are made to primary and/or key secondary hypotheses, or the statistical methods related to those hypotheses, then the protocol will be amended (consistent with ICH Guideline E-9). Post hoc exploratory analyses will be clearly identified in the CSR. No separate Statistical Analysis Plan (SAP) will be issued for this study.

### **7.1 Statistical Analysis Plan Summary**

This section contains a brief summary of the statistical analyses for this trial. Full detail is in the Statistical Analysis Plan (SAP) (Section 7.1.8).

#### **7.1.1 Efficacy Analysis**

The primary and key secondary endpoints, primary analysis population, and statistical methods that will be employed for the efficacy analysis are presented in Table 11 below.

The CR+sCR+VGPR response rate and objective response rate (ORR) per IMWG criteria based on investigator assessment will be conducted in the Full Analysis Set (FAS) population. No multiplicity adjustment is planned.

Table 12: Summary of Analysis Strategy for Key Efficacy Endpoints

Endpoint/Variable (Description, Time point)	Statistical Method	Analysis Population	Missing Data Approach
PFS	Kaplan Meier	FAS	Subjects with missing data are considered non-progressors
CR + sCR + VGPR response rate per IMWG criteria based on	Exact test of binomial parameter	FAS	Subjects with missing data are considered non-responders

investigator assessment			
ORR per IMWG criteria based on investigator assessment	Exact test of binomial parameter	FAS	Subjects with missing data are considered non-responders

### 7.1.2 Safety Analysis

The All-Subjects-as-Treated (ASaT) population will be employed for safety analyses. The ASaT population consists of all subjects who received at least one dose of trial treatment. Subjects who entered the study and did not take any of the study drug(s) and had this confirmed, will not be evaluated for safety.

Descriptive tables that summarize the number and percentage of subjects that experience adverse events as categorized in the NCI CTCAE Version 4 will be generated by dose level.

#### **Stopping rules:**

- Death greater than 10% of patients in any part independent of their relationship to study treatment.
- Grade 4 non-hematologic toxicity in greater than 10% of patients in any part independent of their relationship to study treatment.

The severity of the toxicities will be graded according to the NCI CTCAE v4.0 whenever possible. An interim safety analysis will be performed in between stages 1 and 2 of recruitment (See Section 7.1.3) at the same time as the planned efficacy analysis per the Simon-two-staged design.

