### **6.2.3 Immediate Reporting of Adverse Events to the Sponsor**

#### **6.2.3.1 Serious Adverse Events**

A serious adverse event is any adverse event occurring at any dose or during any use of Merck's product that:

- Results in death;
- Is life threatening;
- Results in persistent or significant disability/incapacity;
- Results in or prolongs an existing inpatient hospitalization;
- Is a congenital anomaly/birth defect;
- Is a new cancer (that is not a condition of the study);
- Is associated with an overdose;
- Is another important medical event

Refer to Table 7 for additional details regarding each of the above criteria.

Any serious adverse event, or follow up to a serious adverse event, including death due to any cause other than progression of the cancer under study that occurs to any subject from the time the consent is signed through 90 days following cessation of treatment, or the initiation of new anti-cancer therapy, whichever is earlier, whether or not related to Merck product, must be reported within 24 hours to the Sponsor and within 2 working days to Merck Global Safety.

Non-serious Events of Clinical Interest will be forwarded to Merck Global Safety and will be handled in the same manner as SAEs.

Additionally, any serious adverse event, considered by an investigator who is a qualified physician to be related to Merck product that is brought to the attention of the investigator at any time outside of the time period specified in the previous paragraph also must be reported immediately to the Sponsor and to Merck.

**SAE reports and any other relevant safety information are to be reported to Georgetown DSMB, Hackensack eIRB, Merck Global Safety ([contact]).**

A copy of all 15 Day Reports and Annual Progress Reports is submitted as required by FDA, European Union (EU), Pharmaceutical and Medical Devices agency (PMDA) or other local regulators. Investigators will cross reference this submission according to local regulations to the Merck Investigational Compound Number (IND, CSA, etc.) at the time of submission. Additionally investigators will submit a copy of these reports to Merck & Co., Inc. (Attn: Worldwide Product Safety; [contact]) at the time of submission to FDA.

All subjects with serious adverse events must be followed up for outcome.

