#### **6.2.4 Evaluating Adverse Events**

An investigator who is a qualified physician will evaluate all adverse events according to the NCI Common Terminology for Adverse Events (CTCAE), version 4.03. Any adverse event which changes CTCAE grade over the course of a given episode will have each change of grade recorded on the adverse event case report forms/worksheets.

All adverse events regardless of CTCAE grade must also be evaluated for seriousness.

Table 11 Evaluating Adverse Events

An investigator who is a qualified physician, will evaluate all adverse events as to:

V4.0 CTCAE Grading	Grade 1	Mild; asymptomatic or mild symptoms; clinical or diagnostic observations only; intervention not indicated.		
	Grade 2	Moderate; minimal, local or noninvasive intervention indicated; limiting age-appropriate instrumental ADL.		
	Grade 3	Severe or medically significant but not immediately life-threatening; hospitalization or prolongation of hospitalization indicated; disabling; limiting self-care ADL.		
	Grade 4	Life threatening consequences; urgent intervention indicated.		
	Grade 5	Death related to AE		

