### **7.1.12 Interim Analysis**

The study will stop and treatment will be rejected if there are 8 or fewer patients are progression free at 12 months. If 9 or more of the first 15 patients have not progressed at 12 months, a further 28 patients will be recruited into the second stage. The optimal design has an expected sample size of 23.5 and probability of early termination of 0.696. If the overall PFS is 70% or above at 12 months, pembrolizumab, lenalidomide and dexamethasone will be considered to have shown worthwhile efficacy. A safety analysis will also be conducted at this time and the study will be terminated if the safety stopping rules are met (See section 7.1.2).

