## **9.7 Data and Safety Monitoring Committee (DSMC)**

The Georgetown Lombardi Comprehensive Cancer Center will be responsible for the data and safety monitoring of this multi-site trial. As this study is an investigator initiated Phase II study utilizing an FDA approved drug for which the PI does not hold the IND it is considered a moderate risk study which requires real-time monitoring by the PI and study team and semi-annual reviews by the LCCC Data and Safety Monitoring Committee (DSMC).

The Principal Investigator and the Co-Investigators will review the data including safety monitoring at their weekly institution based disease group meetings and on monthly disease group teleconferences.

All Severe Adverse Events (SAEs) are required to be reported to the IRB. Based on SAEs, the IRB retains the authority to suspend further accrual pending more detailed reporting and/or modifications to further reduce risk and maximize the safety of participating patients.

Progress on the trial and the toxicities experienced will be reviewed by the LCCC Data and Safety Monitoring Committee every 6 months from the time the first patient is enrolled on the study. Results of the DSMC meetings will be forwarded to the IRB with recommendations regarding need for study closure.

DSMC recommendations should be based not only on results for the trial being monitored as well as on data available to the DSMC from other studies. It is the responsibility of the PI to ensure that the DSMC is kept apprised of non-confidential results from related studies that become available. It is the responsibility of the DSMC to determine the extent to which this information is relevant to its decisions related to the specific trial being monitored.

A written copy of the DSMC recommendations will be given to the trial PI and the IRB. If the DSMC recommends a study change for patient safety or efficacy reasons the trial PI must act to implement the change as expeditiously as possible. In the unlikely event that the trial PI does not concur with the DSMC recommendations, then the LCCC Associate Director of Clinical Research must be informed of the reason for the disagreement. The trial PI, DSMC

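### The toxicity stopping rule names Grade 4 only, so one fatal toxicity without a Grade 4 record plus one Grade 4 case among 15 patients meets neither rule

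*Combined protocol and SAP*

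**What the plan says.** Section 7.1.2 lists two stopping rules. The first is "Death greater than 10% of patients in any part independent of their relationship to study treatment". The second is "Grade 4 non-hematologic toxicity in greater than 10% of patients in any part independent of their relationship to study treatment". The same section places an interim safety analysis between stages 1 and 2, when 15 patients have been accrued (7.1.3). Section 7.1.12 makes the rules binding: "A safety analysis will also be conducted at this time and the study will be terminated if the safety stopping rules are met".

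Table 11 in 6.2.4 separates the two top grades. Grade 4 is "Life threatening consequences; urgent intervention indicated" and Grade 5 is "Death related to AE". Section 6.2.4 also says "Any adverse event which changes CTCAE grade over the course of a given episode will have each change of grade recorded", so a fatal event that passed through Grade 4 should leave a Grade 4 record as well.

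**The concern.** Read as written, the second rule counts Grade 4 and leaves out Grade 5. A fatal toxicity then enters the toxicity count only if its episode was also recorded at Grade 4. The death rule does count it, but in a separate tally with its own 10% limit, and no section pools the two.

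This makes the rules inconsistent in their ordering. Two patients with Grade 4 toxicity among 15 stop the trial. If one of those two instead dies suddenly, with no Grade 4 entry, the outcome is worse but the written rules no longer call for a stop. A binding termination rule should not relax when an outcome gets worse.

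Elsewhere the protocol spells out a range when it means one. Section 7.1.8.2 refers to Grade 3 or above, and the events-of-clinical-interest table in 11.6 uses at-least signs. It is therefore unsafe to assume that Grade 4 here means Grade 4 or worse.

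**Working it through.** **Inputs from the plan.** The limit is more than 10% for each rule (7.1.2). Stage 1 has 15 patients and stage 2 has 28 (7.1.3). Grades 4 and 5 are separate (Table 11). The plan gives no operating characteristics for the safety rules. The efficacy design that supplies the 15 does reproduce: the probability of early termination at a 50% rate is 0.6964, and the expected size is 15 + (1 − 0.6964) × 28 = 23.50, against the stated 0.696 and 23.5.

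**Counts needed.** At n = 15, 1/15 = 6.7% is within the limit and 2/15 = 13.3% exceeds it, so each rule needs two patients. At n = 28, 2/28 = 7.1% is within and 3/28 = 10.7% exceeds it, so each needs three.

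**Two severe cases among 15, in different patients:**

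| Pattern | Death rule | Toxicity rule as written | Grade 4 or 5 pooled |
|---|---|---|---|
| Two Grade 4 | 0/15 | 2/15, stop | 2/15, stop |
| Two fatal | 2/15, stop | depends on Grade 4 records | 2/15, stop |
| One fatal with a Grade 4 record, one Grade 4 | 1/15 | 2/15, stop | 2/15, stop |
| One fatal without a Grade 4 record, one Grade 4 | 1/15 | 1/15, **continue** | 2/15, stop |

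The last row is the only pattern at n = 15 on which the written and pooled rules disagree.

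**How often it occurs.** The documents give no toxicity rates and no share of toxic deaths with a Grade 4 record, so both are assumed. Let p5 and p4 be the risks per patient of Grade 5 and of Grade 4 only, and s the share of toxic deaths with a Grade 4 record. Deaths from other causes are taken as zero. The probability of the disputed pattern is

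15 × 14 × p5(1 − s) × p4 × (1 − p5 − p4)^13.

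At p5 = p4 = 5% and s = 0 this is 210 × 0.05 × 0.05 × 0.9^13 = 0.525 × 0.2542 = 0.133. The pooled rule proceeds with probability 0.9^15 + 15 × 0.10 × 0.9^14 = 0.2059 + 0.3432 = 0.549. The written rules proceed with 0.549 + 0.133 = 0.682 (0.6825 unrounded).

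| Assumed p5 / p4 | s | Proceed, as written | Proceed, pooled | Gap (points) |
|---|---|---|---|---|
| 5% / 5% | 0 | 0.68 | 0.55 | 13.3 |
| 5% / 5% | 50% | 0.62 | 0.55 | 6.7 |
| 5% / 5% | 80% | 0.58 | 0.55 | 2.7 |
| 5% / 5% | 90% | 0.56 | 0.55 | 1.3 |
| 1% / 5% | 0 | 0.82 | 0.77 | 4.7 |
| 1% / 5% | 50% | 0.80 | 0.77 | 2.3 |
| 1% / 5% | 80% | 0.78 | 0.77 | 0.9 |
| 1% / 5% | 90% | 0.78 | 0.77 | 0.5 |

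At s = 100% the gap is zero in both cases.

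**The case against.** The strongest reply is that fatal toxicity already has its own rule. Any-cause death at the same 10% limit is broader than a Grade 5 count, and two separate limits are a legitimate design. The plan never says it meant to cap the combined Grade 4 and 5 rate. What is left is a single pattern, and the grade-change recording in 6.2.4 removes it whenever the fatal episode was also logged at Grade 4. A monitor might in any case read Grade 4 as a floor. The larger gaps also rest on assumed rates.

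The mixed case would not go unseen either. Serious events "must be reported within 24 hours to the Sponsor and within 2 working days to Merck Global Safety" (6.2.3.1). Section 9.7 calls this a "moderate risk study which requires real-time monitoring by the PI and study team", with weekly team review and six-monthly committee review. Section 4.9 allows early termination for a health hazard.

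Most of this stands, and it is why the point is minor. It does not close the gap. None of the oversight provisions sets a number, so none repairs the numeric rule. Nor is the pooled count an outside preference: the plan already treats two Grade 4 cases among 15 as grounds to stop, and the disputed pattern is worse than that.

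**Conclusion.** The point holds as a minor wording defect in a binding rule. On the literal text, exactly one pattern at n = 15 escapes both rules while 13.3% of patients have Grade 4 or 5 non-hematologic toxicity. The effect on the chance of proceeding runs from zero to 13.3 percentage points over the scenarios examined. It is 0.5 to 2.7 points if 80% to 90% of toxic deaths carry a Grade 4 record.

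These sizes depend on assumed toxicity rates, an assumed recording share, no deaths from other causes, and 15 as the denominator at the planned look. The term *any part* is not defined, but reading it as stage 1 gives the same 15. The efficacy analysis is not affected.

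**What to change.** In 7.1.2, change the second rule from Grade 4 to *Grade 4 or 5* and add that each patient counts once. Keep the death rule, the 10% limit and the hematologic exclusion. If Grade 4 alone was intended, one sentence saying so would remove the doubt about the meaning but leave the ordering problem.

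The edit is a few words and the data are already collected. The real cost is that a stricter rule stops a tolerable regimen more often. The table gives the probability of stopping under assumed rates, where s is the share of toxic deaths with a Grade 4 record:

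| Assumed Grade 5 / Grade 4 | Look | As written, s = 0 | As written, s = 80% | Pooled |
|---|---|---|---|---|
| 1% / 2% | n = 15 | 4.5% | 6.7% | 7.3% |
| 2% / 4% | n = 15 | 15.1% | 21.1% | 22.6% |
| 1% / 2% | both stages | 6.5% | 10.8% | 12.0% |
| 2% / 4% | both stages | 25.0% | 37.6% | 40.8% |

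The last two rows apply only if *any part* also covers stage 2, with its 28 patients read separately.

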#### **7.1.4 Responsibility for Analyses**

The statistical analysis of the data obtained from this study will be the responsibility of the Clinical Biostatistician of Hackensack University Medical Center.

The study will be done as an open-label study. The official database will be finalized after medical/scientific review has been performed, protocol violations have been identified, and data have been declared final and complete.

#### **7.1.5 Hypotheses/Estimation**

Objectives and hypotheses of the study are stated in Section 3.0.

#### **7.1.6 Analysis Endpoints**

Efficacy and safety endpoints that will be evaluated by dosing schedules, dose levels, and disease-specific cohorts are listed below.

##### **7.1.6.1 Efficacy Endpoints**

Key efficacy endpoints for the trial include the following as assessed by IMWG:

- PFS: defined as the time from Day 0 of ASCT to progressive disease (PD) or death, whichever occurs earlier, per IMWG criteria by investigator assessment. Subjects without documented PD/death will be censored at the last disease assessment date.
- Complete response, stringent complete response, and very good partial response rate (CR + sCR + VGPR) rate using IMWG criteria. Response rates will be determined with the following baselines 1) Prior to ASCT 2) Cycle 1 day 1 of study drug or screening visit, whichever is higher.
- ORR: Defined as the proportion of subjects who have achieved sCR, CR, VGPR or PR according to the IMWG criteria by investigator assessment. Subjects with missing outcome on objective response will be considered non-responders. Response rates will be determined with the following baselines 1) Prior to ASCT 2) Cycle 1 day 1 of study drug or screening visit, whichever is higher.
- DOR: defined as the time interval between the date of first response (sCR, CR, VGPR, PR) and the date of first documented disease progression.
- TTP: defined as the time from 1) Day 0 ASCT and 2) Date of enrollment to progressive disease (PD) per IMWG criteria by investigator assessment. Subjects without documented PD or death will be censored at the last disease assessment date, and subjects who died without documented PD will be censored at the time of death.

- OS: defined as the time from Day 0 ASCT to death from any cause.

In addition, overall survival (OS) and change from baseline in bone marrow/aspirate PD-L1 expression, T-cell subsets, and cytokine analysis will be evaluated.

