#### 3.2.1.2 Rationale for Evaluating anti-PD-1 Therapy in Patients with High-Risk Multiple Myeloma Post High-Dose Chemotherapy followed by Peripheral Blood Autologous Stem Cell Transplant

Overall survival in MM ranges from several months to greater than 15 years. With modern therapy, survival in MM has increased from a median overall survival (OS) of 3–5 years to a 5-year survival rate of greater than 70% in transplant-eligible patients[40]. The improvement in survival, however, is not universal, and approximately 25% of patients have a median survival of 2 years or less[41]. The definition of high-risk MM has been in considerable flux. Some of the largest studies have used International Staging System

(ISS) and the presence of chromosome 13q abnormalities by cytogenetics as the primary definition[42]. The revised-ISS (R-ISS) combines ISS 3, high-risk cytogenetics, and elevated LDH as markers for inferior survival[43]. More recently, p53 deletions have been associated with PFS of 11.8 months[44]. Patients with high-risk gene expression profiling (GEP)-70 scores (and patients with chromosome 1q amplifications and 1p deletions by fluorescent in situ hybridization (FISH) show similar patterns[45]. Internal data from the Hackensack University Medical Center Multiple Myeloma division show that high-risk MM patients defined as those carrying 1q amplifications, 1p deletions, 13q deletions by cytogenetics, p53 deletions, high-risk GEP 70 scores, t(4;14), t(14;16) and t(14;20), hypodiploidy have a median event free survival (EFS) of 14 months post ASCT. The MRC IX trial showed that patients with high-risk MM by FISH have a 50% 12-month PFS from transplant[46].

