### **3.2.3 Rationale for Endpoints**

#### **3.2.3.1 Efficacy Endpoints**

The primary efficacy objective of this trial is to determine Progression Free Survival (PFS) from the date of ASCT, with day 0 defined as date of stem cell infusion (if tandem transplant the 2nd of 2 transplants will be used) until the date of progression, defined as the date at which the patient starts the next line of therapy or the date of death. The Overall Survival (OS) will also be calculated from the date of ASCT as previously defined until the date of death.

The secondary efficacy objective of this trial is to evaluate the anti-tumor activity of pembrolizumab (MK-3475), lenalidomide and dexamethasone in subjects with high-risk MM post-ASCT. This will be complete response (CR) + stringent complete response (sCR) + very good partial response (VGPR) rate and objective response rate (ORR) as assessed by the investigator per International Myeloma Working Group (IMWG) uniform response criteria for MM[57].

Immunotherapeutic agents such as pembrolizumab (MK-3475), lenalidomide and dexamethasone may produce anti-tumor effects by potentiating endogenous cancer-specific immune responses, which may be functionally anergic. The response patterns seen with such an approach may extend beyond the typical time course of responses seen with cytotoxic agents, and can manifest a clinical response after an initial increase in tumor burden or even the appearance of new lesions. Standard response assessment criteria may not provide a comprehensive response assessment of immunotherapeutic agents such as pembrolizumab (MK-3475), lenalidomide and dexamethasone. Disease response assessment will be performed every 21-day treatment cycles. PD must be confirmed prior to discontinuation from study.

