#### 4.1.2 Subject Inclusion Criteria

In order to be eligible for participation in this trial, the subject must:

1. Be willing and able to provide written informed consent/assent for the trial.
2. Be  $\geq 18$  years of age on day of signing informed consent.
3. Has a confirmed diagnosis of MM based on standard criteria. (See Appendix 2 for MM Diagnostic Criteria.)

4. Is between 60 and 180 days from peripheral blood autologous stem cell transplant.

5. At diagnosis, had MM with measurable disease, defined as:

- A monoclonal immunoglobulin spike on serum electrophoresis of at least 0.5 g/dL and/or
- Urine monoclonal levels of at least 200 mg/24 hours
- For subjects without measurable serum and urine M-protein levels, an abnormal free light chain (FLC) ratio (normal value 0.26 – 1.65) with involved FLC  $\geq 10$  mg/dL
- Radiographic evidence of disease for those without measurable M-spike or free light chains.

6. Has high-risk MM, which must be present at the time of diagnosis, and defined by:

- a. International Staging System (ISS) stage 3 (See Appendix 3 for ISS Staging), and/or
- b. Deletion 13q by cytogenetics, and/or
- c. 1q amplification, 1p deletion, p53 deletions (17p deletions), t(4;14), t(14;16), t(14;20), hypodiploidy, and/or
- d. High-risk gene expression profile (GEP) scores

7. Be able to provide a newly obtained bone marrow aspirate/biopsy material for biomarker analysis and disease assessment.

8. Have a performance status of  $\leq 2$  on the ECOG Performance Scale (See Appendix 4).

9. Demonstrate adequate organ function as defined in Table 1, all screening labs should be performed within 28 days of treatment initiation.

Table 1 Adequate Organ Function Laboratory Values

System	Laboratory Value
Hematological	
Absolute neutrophil count (ANC)	$\geq 1,000$ /mcL
Platelets	$\geq 75,000$ / mcL
Hemoglobin	$\geq 8$ g/dL or $\geq 5.6$ mmol/L without transfusion or EPO dependency (within 7 days of assessment)
Renal	
Serum creatinine OR Measured or calculated a creatinine clearance (GFR can also be used in place of creatinine or CrCl)	$\leq 1.5$ X upper limit of normal (ULN) OR $\geq 60$ mL/min for subject with creatinine levels $> 1.5$ X institutional ULN
Hepatic	

Serum total bilirubin	
	$\leq 1.5 \times \text{ULN}$ OR
	Direct bilirubin $\leq \text{ULN}$ for subjects with total bilirubin levels $> 1.5 \text{ ULN}$
AST (SGOT) and ALT (SGPT)	

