#### 4.1.3 Subject Exclusion Criteria

The subject must be excluded from participating in the trial if the subject:

1. Is currently participating and receiving study therapy or has participated in a study of an investigational agent and received study therapy or used an investigational device within 4 weeks of the first dose of treatment.

Pembrolizumab (MK-3475), [name], HUMC

2. Has a diagnosis of immunodeficiency or is receiving systemic steroid therapy or any other form of immunosuppressive therapy within 7 days prior to the first dose of trial treatment. The use of physiologic doses of corticosteroids may be used at the investigator's discretion.
3. Has received an allogeneic stem cell transplant.
4. Has received any myeloma-directed therapy after ASCT.
5. Has a known history of active TB (Bacillus Tuberculosis)
6. Hypersensitivity to pembrolizumab or any of its excipients.
7. Progressive disease from autologous transplantation at the time of screening. See Appendix 11.5 for criteria
8. Has known active central nervous system (CNS) metastases and/or carcinomatous meningitis. Subjects with previously treated brain metastases may participate provided they are stable (without evidence of progression by imaging for at least four weeks prior to the first dose of trial treatment and any neurologic symptoms have returned to baseline), have no evidence of new or enlarging brain metastases, and are not using steroids for at least 7 days prior to trial treatment. This exception does not include carcinomatous meningitis which is excluded regardless of clinical stability.
9. Has active autoimmune disease that has required systemic treatment in the past 2 years (i.e. with use of disease modifying agents, corticosteroids or immunosuppressive drugs). Replacement therapy (eg., thyroxine, insulin, or physiologic corticosteroid replacement therapy for adrenal or pituitary insufficiency, etc.) is not considered a form of systemic treatment.
10. Has a history of (non-infectious) pneumonitis that required steroids or current pneumonitis.
11. Has an active infection requiring intravenous systemic therapy.
12. Has a history or current evidence of any condition, therapy, or laboratory abnormality that might confound the results of the trial, interfere with the subject's participation for the full duration of the trial, or is not in the best interest of the subject to participate, in the opinion of the treating investigator.

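### PFS is timed from transplant but patients enter event-free at day 60 to 180, and the 50% null states neither its source nor whether it carries the same condition

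*Combined protocol and SAP*

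**What the plan says.** **Clock.** Section 7.1.6.1 has PFS "defined as the time from Day 0 of ASCT to progressive disease (PD) or death, whichever occurs earlier". Section 3.2.3.1 agrees: "Progression Free Survival (PFS) from the date of ASCT, with day 0 defined as date of stem cell infusion", using the second infusion for tandem transplants.

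**Entry.** Section 4.1.2, item 4: "Is between 60 and 180 days from peripheral blood autologous stem cell transplant". Section 4.1.3 excludes patients with "Progressive disease from autologous transplantation at the time of screening" (item 7) and any patient who "Has received any myeloma-directed therapy after ASCT" (item 4). Section 7.1.7.1 analyses PFS in all enrolled subjects.

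**Null and rule.** Sections 7.1.3 and 7.1.10 set a Simon two-stage design with p0 = 50%, p1 = 70%, one-sided 5% error and 80% power, and give no source for p0. Sections 7.1.3 and 7.1.12 continue to stage two with at least 9 of 15 patients progression-free at 12 months. Section 7.1.3 then rejects the null with at least 27 of 43. The stated early-stopping probability is 0.696 and the expected sample size 23.5.

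**Historical figures.** The control is historical (Trial Summary). Section 3.2.1.2 reports: "The MRC IX trial showed that patients with high-risk MM by FISH have a 50% 12-month PFS from transplant". It also says that "p53 deletions have been associated with PFS of 11.8 months", and that high-risk patients in the centre's own series "have a median event free survival (EFS) of 14 months post ASCT".

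**The concern.** Each analysed patient brings roughly two to six months of PFS time that had passed before study treatment and was nearly event-free by selection. The exception is small: progression that emerges, or is confirmed, only after screening, since Appendix 11.5 requires two consecutive assessments.

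A historical rate counted from transplant with no such condition includes patients who progressed or died in those months and could never have enrolled. Comparing the trial with that rate credits the selection to the treatment. No section sets a landmark, a delayed-entry analysis or a conditional null.

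At stake are the chance that an inactive regimen passes the final rule and the chance that it is stopped after 15 patients.

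**Working it through.** **1. Reproduce the stated design.** Inputs from Sections 7.1.3 and 7.1.12: n1 = 15, continue if X1 ≥ 9, N = 43, reject if X1 + X2 ≥ 27.

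- P(stop early | p) = P(Bin(15, p) ≤ 8)
- P(reject | p) = Σ over x = 9 to 15 of P(Bin(15, p) = x) × P(Bin(28, p) ≥ 27 − x)

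At p = 0.50, early stopping is 0.696, expected N is 15 + (1 − 0.696) × 28 = 23.5, and the error is 0.0499. At p = 0.70, power is 0.804. This is the stated design. The error reaches 0.05 at p = 0.50005, so there is no room for a higher null.

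**2. Null for enrollable patients.** Let L be the share of benchmark patients with an event before the trial's entry time. If 50% is the unconditioned 12-month rate and the benchmark is otherwise comparable:

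p0* = P(event-free at 12 months) / P(event-free at entry) = 0.50 / (1 − L)

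**3. Effect on the 27-of-43 rule.** L is not in the documents, so these values are assumptions.

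| Assumed L | p0* | Error (stated 0.05) | Early stopping (stated 0.696) |
|---|---|---|---|
| 2% | 0.50/0.98 = 0.510 | 0.065 | 0.67 |
| 5% | 0.50/0.95 = 0.526 | 0.095 | 0.62 |
| 10% | 0.50/0.90 = 0.556 | 0.172 | 0.53 |

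**4. Case mix needed to cancel this.** The true unconditioned rate in this population would have to be 0.50 × (1 − L), that is 0.49, 0.475 or 0.45. The documents point both ways: 11.8 months for p53 deletion, but a 14-month median EFS in the centre's series, which by definition of a median puts 12-month EFS at or above 50%.

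**5. The separate 70% criterion.** Sections 1.1, 7.1.3 and 7.1.12 also ask for 12-month PFS of at least 70%. Since 0.70 × 43 = 30.1, this means at least 31 of 43. Its error is 0.004, 0.007 and 0.019 at L = 2%, 5% and 10%, and 0.049 at L = 15% (p0* = 0.588). Its power at 70% is 0.445.

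**The case against.** **The link is inferred.** No section says that p0 came from the from-transplant figure. Section 2.1 words the 70% target for patients receiving the consolidation, who have already passed screening, and Section 7.1.3 pairs p0 with p1. A natural reading puts both in the enrolled population, and then the error is 0.0499 as stated. This stands. A reader might infer that the trial's type I error is inflated as a matter of fact. The documents do not show that. They show that p0 has no stated source or risk set, and that the one matching figure carries no event-free condition.

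**The net bias is unknown.** The benchmark is high risk by FISH. The trial also admits patients on ISS stage 3, deletion 13q by cytogenetics or gene expression scores, and restarts the clock at a second transplant. Case mix could offset or enlarge the effect. This also stands, although the plan makes no such argument.

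**Much larger errors are possible only under assumed curves.** A constant hazard through 50% at 12 months, with entry uniform over days 60 to 180, gives 0.49, and a reader might quote it. It implies 24-month PFS of 25%. Section 3.2.1.2 instead describes relapse within one to two years of first transplant and almost no long-term remitters, which favours a rising hazard. Weibull shapes 2 to 3 give 0.13 to 0.07. That passage counts from first transplant, so even this is only indicative.

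**The 70% criterion is stricter.** It limits the inflation, but the stated 5% and 80% belong to 27 of 43. Which criterion governs is a separate issue.

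**The 59% in Section 7.1.3 might be taken for a conditioned null.** It does not fit: at 0.59 the rule rejects with probability 0.304.

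**TTP from enrolment is also planned.** It is secondary and censors deaths, so it does not correct the primary test.

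**Conclusion.** The point holds in conditional form. The clock, the entry conditions and the absence of a source or risk set for p0 are plain in the documents. If p0 is the unconditioned from-transplant rate and the benchmark is otherwise comparable, the direction follows by arithmetic: any L above about 0.01% takes the 27-of-43 rule past 5%.

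The size rests on L, which is not given; the table covers assumed values of 2% to 10%, with no single best estimate. If p0 already refers to patients event-free at entry, the stated error is correct and the plan only needs to say so. It should be fixed, with medium confidence.

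**What to change.** In Sections 7.1.3 and 7.1.10, state where p0 comes from and which patients it describes. If it is already conditional on being event-free at entry, one sentence with the source settles the matter.

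If it is not, keep ASCT as time zero and replace p0 with the 12-month rate among historical high-risk patients alive, progression-free and untreated at the trial's entry times, for example from the centre's own series. Say whether the 70% target already refers to enrolled patients. Then restate the final threshold, error, power and early-stopping probability at 43 patients.

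The direct cost is wording and a historical data extract. The statistical cost depends on p1. Keeping N = 43 and the 9-of-15 stage-one rule:

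| Assumed L | Final threshold | Error | Power, p1 = 0.70 | Power, p1 = 0.70/(1 − L) |
|---|---|---|---|---|
| 2% | 28 of 43 | 0.037 | 0.75 | 0.81 (p1 = 0.714) |
| 5% | 29 of 43 | 0.032 | 0.67 | 0.83 (p1 = 0.737) |
| 10% | 30 of 43 | 0.038 | 0.565 | 0.91 (p1 = 0.778) |

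So 43 patients keep 80% power only if p1 is conditioned in the same way. The wording of Section 2.1 suggests that p1 stays at 0.70. The lower power then has to be stated and accepted, or the sample size reconsidered.
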